## **13 REGISTRATION GUIDELINES**

When the clinical research coordinator (CRC) or study coordinator (SC) identifies a potential study patient, they MUST contact the Research Compliance Office at the Huntsman Cancer Institute (by

email at [[contact]](mailto:[contact])) to confirm that a slot is available prior to initiating the consent process.

After a patient has consented to participate in the study and all screening procedures have been completed, the CRC/SC will review eligibility with the properly delegated enrolling physician who will sign a copy of the eligibility checklist (section 5). This, along with all de-identified documentation supporting eligibility, will be sent to the RCO at HCI for verification.

Eligible patients will be registered on study at the University of Utah – Huntsman Cancer Institute and applicable subsites via the OnCore system by the CRC/SC. **Patients must meet all of the eligibility requirements listed in Section 5 prior to registration.**

Following registration, patients should begin protocol treatment within 5 days. Issues that would cause treatment delays should be discussed with the principal investigator. If a patient does not receive protocol therapy following registration, the patient's registration on the study may be canceled. The CRC/SC and Research Compliance Office should be notified of cancellations as soon as possible.

Once the RCO confirms the patient's eligibility and notifies the CRC/SC, the patient can be registered by emailing a completed Clinical Trials Office Patient Registration Form to the RCO at [[contact]](mailto:[contact]). The RCO will then return the completed form (including patient number and cohort/dose level) to the coordinator after which time the patient can begin treatment.

**Patients must meet all of the eligibility requirements listed in Section 5 prior to registration.**

**Study related screening procedures can only begin once the patient has signed a consent form. Patients must not begin protocol treatment prior to registration.**

## 14 DATA SUBMISSION SCHEDULE

The Case Report Forms (CRFs) are a set of (electronic or paper) forms for each patient that provides a record of the data generated according to the protocol. CRF's should be created prior to the study being initiated and updated (if applicable) when amendments to the protocol are IRB approved. These forms will be completed on an on-going basis during the study. The medical records will be source of verification of the data. During the study, the CRFs will be monitored for completeness, accuracy, legibility and attention to detail by a member of the Research Compliance Office. The CRFs will be completed by the Investigator or a member of the study team as listed on the Delegation of Duties Log. The data will be reviewed no less than annually by the Data and Safety Monitoring Committee. The Investigator will allow the Data and Safety Monitoring Committee or Research Compliance Office personnel access to the patient source documents, clinical supplies dispensing and storage area, and study documentation for the above-mentioned purpose. The Investigator further agrees to assist the site visitors in their activities.

Data capture should be restricted to endpoints and relevant patient information required for planned manuscripts.

## **15 SPECIAL INSTRUCTIONS**

### **15.1 Pathology review for PD-L1 analysis at central laboratory**

Formalin fixed paraffin embedded (FFPE) tissue samples will be sent for PD-L1 IHC analysis at screening if samples are available. Fine needle aspirate, frozen sample, plastic embedded sample, cell block, clot, bone, bone marrow or cytologic specimens will not be accepted for PD-L1 IHC analysis. If a patient does not have archival tissue available and a fresh biopsy is required for Ki-67 testing (see 15.3), tissue will be sent for PD-L1 analysis if adequate tissue is available after Ki-67 testing has been performed. This is optional when tissue is available for evaluation.

If the patient consents to this testing, screening tissue samples will be sent to QualTek Molecular Laboratories.

Please reference the Qualtek lab manual for more information.

### **15.2 Pathology review for tumor mutational burden analysis**

Screening tissue analyzed for correlation of tumor mutational burden will be performed locally per treatment center's standard protocol. If not performed previously and not clinically indicated at the time of screening, TMB will not be required.

### **15.3 Pathology review for Ki-67 antibody staining**

Patients must have existing Ki-67 results from archival tissue or available tissue for Ki-67 testing. If no archival tissue is available the subject must agree to a fresh biopsy for testing to qualify for the study.

Screening tissue Ki-67 immunohistochemistry will be performed locally per treatment center's standard protocol.

### **15.4 Correlative Studies**

#### **15.4.1 Tissue Specimens for PD-L1 IHC analysis**

- 5 unstained slides cut at 4 microns thickness.

##### **15.4.1.1 Fresh tissue biopsy (if archival tissue is not available for Ki-67 testing)**

- 1-2 cores with an 18 gauge needle.
- .

## **16 ETHICAL AND REGULATORY CONSIDERATIONS**

### **16.1 Recruitment Strategies**

Potential patients will be identified by Investigators in the setting of their outpatient clinics.

## **16.2 Informed consent**

Informed consent will be obtained from all research participants prior to performing any study procedures using the most recent IRB approved version.

## **16.3 Human Subjects Protections**

### **16.3.1 Participation of Children**

Patients must be at least 18 years of age to participate.

### **16.3.2 Participation of Subjects Unable To Give Consent**

Patients unable to give consent will be allowed to participate if a legally authorized representative (as defined by Utah state laws and the policy of the IRB) consents on their behalf.

## **16.4 Institutional Review**

Study will be approved by the Institutional Review Board of University of Utah.

## **16.5 Data and Safety Monitoring Plan**

A Data and Safety Monitoring Committee (DSMC) is established at Huntsman Cancer Institute (HCI) and approved by the NCI to assure the well-being of patients enrolled on Investigator Initiated Trials that do not have an outside monitoring review. Roles and responsibilities of the DSMC are set forth in the NCI approved plan. The activities of this committee include a quarterly review of adverse events including SAEs, important medical events, significant revisions or amendments to the protocol, and approval of cohort/dose escalations. If the DSMC and/or the PI have concerns about unexpected safety issues, the study will be stopped and will not be resumed until the issues are resolved. The DSMC also reviews and approves audit reports generated by the Research Compliance Office.

All phase II studies are reviewed by the full committee at each quarterly DSMC meeting. This includes a review of all serious adverse events (SAEs) occurring in patients treated at HCI or its affiliates as well as toxicities for patients on treatment and within a 30 day follow-up window.

## **16.6 Adverse Events / Serious Adverse Events**

This study will utilize the CTCAE (NCI Common Terminology Criteria for Adverse Events) Version 4.0 for AE and SAE reporting.

### **16.6.1 Adverse Events (AEs)**

An adverse event is the appearance or worsening of any undesirable sign, symptom, or medical condition occurring after starting the study drug even if the event is not considered to be related to study drug. For the purposes of this study, the terms toxicity and adverse event are used interchangeably. Medical conditions/diseases present before starting study drug are only considered adverse events if they worsen after starting study drug. Abnormal laboratory values or test results constitute adverse events only if they induce clinical signs or symptoms, are considered clinically significant, or require therapy.

The collection of adverse events will begin after the first dose of study treatment and end 30 days post the last dose of study treatment.

Information about all adverse events, whether volunteered by the subject, discovered by investigator questioning, or detected through physical examination, laboratory test or other means, will be collected and recorded and followed as appropriate.

The occurrence of adverse events should be sought by non-directive questioning of the patient at each visit or phone contact during the study. Adverse events also may be detected when they are volunteered by the patient during or between visits or through physical examination, laboratory test, or other assessments. As far as possible, each adverse event should be evaluated to determine:

1. The severity grade based on CTCAE v.4 (grade 1-5)
2. Its relationship to the study drug(s) (definite, probable, possible, unlikely, not related)
3. Its duration (start and end dates or if continuing at final exam)
4. Action taken (no action taken; study drug dosage adjusted/temporarily interrupted; study drug permanently discontinued due to this adverse event; concomitant medication taken; non-drug therapy given; hospitalization/prolonged hospitalization)
5. Whether it constitutes an SAE

All adverse events will be treated appropriately. Such treatment may include changes in study drug treatment as listed in the dose modification section of this protocol (see section 8 for guidance). Once an adverse event is detected, it should be followed until its resolution, and assessment should be made at each visit (or more frequently, if necessary) of any changes in severity, the suspected relationship to the study drug, the interventions required to treat it, and the outcome.

Information about common side effects already known about the investigational and commercial drugs are described in the Drug Information (section 3) and the most recent Investigator Brochure or the FDA-approved product labels. This information will be included in the patient informed consent and will be discussed with the patient during the study as needed.

All adverse events will be immediately recorded in the patient research chart.

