## **7.8 Duration of Therapy**

A subject must be discontinued from the trial for any of the following reasons:

- The subject or legal representative (such as a parent or legal guardian) withdraws consent.
- Radiographic disease progression by irRECIST (progression must be confirmed with follow up scan no less than 4 weeks and no more than 8 weeks after the first scan shows disease progression)
- Unacceptable adverse experiences as described in Section 8.1
- Intercurrent illness that prevents further administration of treatment
- Investigator's decision to withdraw the subject
- The subject has a confirmed positive serum pregnancy test
- Noncompliance with trial treatment or procedure requirements
- The subject is lost to follow-up
- Completed 24 months of uninterrupted treatment with pembrolizumab or 35 administrations of study medication, whichever is later.

*Note: 24 months of study medication is calculated from the date of first dose.*

- Administrative reasons

The End of Treatment and Follow-up visit procedures are listed in Section 9 (Protocol Calendar). After the end of treatment, each subject will be followed for 30 days for adverse event monitoring (serious adverse events will be collected for 90 days after the end of treatment or until a new cancer treatment is started, if sooner). Subjects who discontinue for reasons other than progressive disease will have post-treatment follow-up for disease status until disease progression, initiating a non-study cancer treatment, withdrawing consent or becoming lost to follow-up. After documented disease progression each subject will be followed for overall survival, withdrawal of consent, or the end of the study, whichever occurs first.

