### **8.1 Dose modification and toxicity management guidelines for pembrolizumab**

#### **8.1.1 Dose modification and toxicity management for immune-related AEs associated with Pembrolizumab**

AEs associated with pembrolizumab exposure may represent an immunologic etiology. These immune-related AEs (irAEs) may occur shortly after the first dose or several months after the last dose of pembrolizumab treatment and may affect more than one body system simultaneously. Therefore, early recognition and initiation of treatment is critical to reduce complications. Based on existing clinical trial data, most irAEs were reversible and could be managed with interruptions of pembrolizumab, administration of corticosteroids and/or other supportive care. For suspected irAEs, ensure adequate evaluation to confirm etiology or exclude other causes. Additional procedures or tests such as bronchoscopy, endoscopy, skin biopsy may be included as part of the evaluation. Based on the severity of irAEs, withhold or permanently discontinue pembrolizumab and administer corticosteroids. Dose modification

and toxicity management guidelines for irAEs associated with pembrolizumab are provided in Table 3.

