### **16.6.2 Serious Adverse Event (SAE)**

Information about all serious adverse events will be collected and recorded. A serious adverse event is an undesirable sign, symptom or medical condition which:

- Is fatal or life-threatening
- Results in persistent or significant disability/incapacity
- Is medically significant, i.e., defined as an event that jeopardizes the patient or may require medical or surgical intervention to prevent one of the outcomes listed above
- Causes congenital anomaly or birth defect
- Requires inpatient hospitalization or prolongation of existing hospitalization, unless hospitalization is for:

- Routine treatment or monitoring of the studied indication, not associated with any deterioration in condition (procedures such as central line placements, paracentesis, pain control)
- Elective or pre-planned treatment for a pre-existing condition that is unrelated to the indication under study and has not worsened since the start of study drug
- Treatment on an emergency outpatient basis for an event not fulfilling any of the definitions of a SAE given above and not resulting in hospital admission
- Social reasons and respite care in the absence of any deterioration in the patient's general condition

Collection of serious adverse events will begin after the first dose and end 90 days after the last dose of study treatment or until a new cancer treatment is initiated, whichever happens the soonest.

Any death from any cause while a patient is receiving treatment on this protocol or up to 30 days after the last dose of protocol treatment, or any death which occurs more than 30 days after protocol treatment has ended but which is felt to be treatment related, must be reported.

Toxicities which fall within the definitions listed above must be reported as an SAE regardless if they are felt to be treatment related or not. Toxicities unrelated to treatment that do NOT fall within the definitions above, must simply be documented as AEs in the patient research chart.

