## **16.8 Events of Clinical Interest (ECI)**

Selected non-serious and serious adverse events thought to be related to Pembrolizumab are also known as Events of Clinical Interest (ECI) and must be recorded as such on the Adverse Event case report forms/worksheets and reported within 24 hours to the HCI Principal Investigator and research compliance office and within 2 working days of first knowledge or notification of event to Merck Global Safety. (Attn: Worldwide Product Safety; [contact] or [AER\\[contact]](mailto:[contact]))

Events of clinical interest for this trial include:

1. An overdose of Merck product, as defined in Section 16.7 - Definition of an Overdose for This Protocol and Reporting of Overdose to the Sponsor, that is not associated with clinical symptoms or abnormal laboratory results.
2. An elevated AST or ALT lab value that is greater than or equal to 3X the upper limit of normal and an elevated total bilirubin lab value that is greater than or equal to 2X the upper limit of normal and, at the same time, an alkaline phosphatase lab value that is less than 2X the upper limit of normal, as determined by way of protocol-specified laboratory testing or unscheduled laboratory testing.\*

**\*Note:** these criteria are based upon available regulatory guidance documents. The purpose of the criteria is to specify a threshold of abnormal hepatic tests that may require an additional evaluation for an underlying etiology.

ECIs that occur in any subject from the date of first dose through 90 days following cessation of treatment, or the initiation of a new anticancer therapy, whichever is earlier, whether or not related to the Merck's product, must be reported within 24 hours to the HCI and to Merck Global Safety within 2 working days of first knowledge or notification of event

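### Non-serious adverse events are collected only to day 30 after the last dose, so new late-onset immune-related events that are neither serious nor listed ECIs drop out of the safety table

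*Combined protocol and SAP*

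**What the plan says.** **Adverse events in general.** Under Section 16.6.1 collection starts after the first dose and is to "end 30 days post the last dose of study treatment". Section 7.8 agrees: after treatment ends, "each subject will be followed for 30 days for adverse event monitoring".

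**Serious adverse events.** Under Section 16.6.2 collection is to "end 90 days after the last dose of study treatment or until a new cancer treatment is initiated, whichever happens the soonest".

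**Events of clinical interest.** Section 16.8 requires reporting of "ECIs that occur in any subject from the date of first dose through 90 days following cessation of treatment", or until new anticancer therapy if that comes earlier. It lists two: an overdose "that is not associated with clinical symptoms or abnormal laboratory results", and a combined transaminase and bilirubin elevation without a matching rise in alkaline phosphatase.

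**Timing of immune-related events.** Section 8.1.1 says these events "may occur shortly after the first dose or several months after the last dose of pembrolizumab treatment".

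**Use of the data.** Safety and tolerability is a secondary objective (Section 1.2.4). Section 12 plans a tabulation of adverse events, with no separate immune-related or late-onset category.

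**The concern.** The toxicity most specific to this drug class is immune-related, and the protocol itself says that it can begin well after dosing stops. The window for non-serious events nevertheless closes at day 30, while sites must still look for serious events and ECIs until day 90. An immune-related event that begins in between, and qualifies as neither, has no route into the dataset. The safety table would then understate how often such events occur. A reader of the results could not tell that from the table, because the analysis section does not say where counting stops.

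**Working it through.** The plan states no figure to reproduce. The check compares the windows, then asks whether any other route captures the event.

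**1. Windows after the last dose**

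| Event type | Section | Collected to |
|---|---|---|
| Non-serious AE, not an ECI | 16.6.1, 7.8 | day 30 |
| SAE | 16.6.2, 7.8 | day 90, or new cancer treatment if sooner |
| Listed ECI, serious or not | 16.8 | day 90, or new anticancer therapy if sooner |
| Stated possible onset of immune-related AEs | 8.1.1 | several months |

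Gap for non-serious events that are not ECIs: 90 - 30 = 60 days (days 31-90). This is a maximum, because the 90-day window closes at new therapy.

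**2. Other routes into the data**

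- *SAE definition (16.6.2).* It is wider than hospital admission and includes medically significant events, so some Grade 3 immune-related events managed without admission would be collected. Lower-severity events generally would not.
- *ECI list (16.8).* The liver pattern is caught. An isolated transaminase rise, thyroid disease, or a non-serious skin, bowel or lung event is not.
- *Study calendar (Section 9).* The row for review of adverse events and ECIs is marked through End of Treatment and is blank under Follow-up.
- *Concomitant medications (7.7.1).* After day 30 they are recorded only for SAEs and ECIs, so treatment records would not reveal the event later.
- *DSMC review (16.5).* Toxicities are reviewed on treatment and for 30 days.
- *Follow to resolution (16.6.1).* An event detected before the cutoff is followed until it resolves, so only new onsets are lost.

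None of these captures a new, non-serious, non-ECI immune-related event on days 31-90.

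**3. Scale of the gap in time**

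- Share of the post-treatment SAE window: 60 / 90 = 67%.
- Share of total SAE observation, using the average of about 24 weeks on treatment in Section 4.4 (24 x 7 = 168 days): 60 / (168 + 90) = 60 / 258 = 23%.

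Both are shares of time. Neither measures the proportion of events missed.

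**4. Illustration only**

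The documents give no rate of late-onset events. Let q be an *assumed* share of patients with a new event of this kind that goes uncollected, and n the number of patients, taken as 34 to 40 from Section 12. Expected patients missed = n x q; chance of missing at least one = 1 - (1 - q)^n.

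| Assumed q | Patients missed (n = 34 to 40) | Chance of missing at least one |
|---|---|---|
| 2% | 0.7 to 0.8 | 50% to 55% |
| 5% | 1.7 to 2.0 | 83% to 87% |
| 10% | 3.4 to 4.0 | 97% to 99% |
| 20% | 6.8 to 8.0 | over 99% |

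**The case against.** The strongest reply is that this is a deliberate and consistent design. Section 7.8 states the 30-day and 90-day windows together, Sections 16.6.1 and 16.6.2 repeat them, and the DSMC window in Section 16.5 agrees with the shorter one. Safety has no comparator, hypothesis or decision rule, and a table of events to day 30 is a well-defined summary. That stands: the windows do not contradict one another, and the point is about fit to the stated latency.

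The reply is also right that coverage beyond day 30 is not nil, given the SAE criterion for medically significant events and the liver ECI. The scope of ECIs may be wider than the two listed items: Section 16.8 introduces its list as what ECIs include, and Section 7.7.2 refers to an ECI with a suspected immune cause, although Section 16.8 names no such category. This ambiguity could lead sites to record late events differently, so it is a reason to clarify the text.

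Finally, the calendar schedules no day-90 visit, and its Follow-up column has no chemistry or thyroid tests. Longer collection would therefore find laboratory-detected events unevenly. That limits what the change can achieve. It does not remove the case for recording events that come to light, since sites must already ascertain SAEs and ECIs to day 90.

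**Conclusion.** The gap is real and its direction is certain: the planned tabulation can only err low for new, non-serious immune-related events on days 31-90 that meet neither an SAE criterion nor a listed ECI. The loss falls mainly on lower-severity events, its size cannot be derived from the documents, and the primary response endpoint is untouched. This is a worthwhile low-cost improvement, not a serious flaw.

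Four stronger readings that a reader might infer are not supported:

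- *Late events are to be expected.* Section 8.1.1 gives a possible timing and no frequency.
- *Every Grade 3 event without admission is missed.* Some would qualify as medically significant SAEs, and some liver events as ECIs.
- *Two thirds of late events are lost.* The 67% is a share of the post-treatment window, which can close early at new therapy.
- *Patients who stop early are worst affected.* Nothing in the documents shows this. Those who stop for progression may start new therapy, which would end the longer window too.

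The conclusion assumes that the ECI list in Section 16.8 is complete as written. If the wider sense suggested by Section 7.7.2 is intended, part of the gap to day 90 closes. Beyond day 90 no routine collection is planned on either reading, apart from reports of deaths thought to be treatment related.

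**What to change.** - In Sections 16.6.1 and 7.8 and in the study calendar, keep 30 days for other non-serious events. Record reported immune-related events in the Table 3 categories, serious or not, to 90 days after the last dose or new anticancer therapy, whichever is sooner. Use the contacts already needed for SAE and ECI collection, with no added tests.
- In Section 12, tabulate these events separately. State that other non-serious events are counted to day 30, that laboratory-detected events after treatment may be incompletely captured, and that events after day 90 are not counted.
- Reconcile the reference in Section 7.7.2 to an ECI of suspected immune cause with the list in Section 16.8.

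The cost is a little more data entry. The change concerns data collection and reporting only. Day 90 matches the existing SAE and ECI window; it does not cover the whole latency that Section 8.1.1 allows for, which is why the limitation should be stated.
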